9.1.1 Dose Escalation and Expansion

A classical “3+3” study design will be used to estimate the MTD for CAR-specific T cells treatment among patients with newly-diagnosed WHO grade IV malignant glioma. As shown below in [Table 3](#), 4 dose levels will be considered based on transduced cells/kg: #1: 4.5 x 10⁶/kg, #2: 1.5 x 10⁷/kg, #3: 4.5 x 10⁷/kg, and #4: 1.5 x 10⁸/kg.

Table 3. Dose Escalation and Expansion

Dose Escalation and Expansion			
Cohort	Dose of CAR-specific T cells	# of Subjects	Schema
1	4.5 x 10 ⁶ /kg	3-6	Dose escalation: “Standard 3+3”
2	1.5 x 10 ⁷ /kg	3-6	
3	4.5 x 10 ⁷ /kg	3-6	
4	1.5 x 10 ⁸ /kg *	3-6	
* If the patient’s targeted dose is 1.5 x 10 ⁸ /kg (dose level #4), the calculated dose will be capped at 1.0 x 10 ¹⁰ total cells.			

Starting with the lowest dose level, cohorts of 3-6 subjects will be accrued at each dose level according to the following dose escalation rules:

Table 4. Dose Escalation Rules

Number of patients with DLT observed during the first 4 weeks after CAR treatment	Escalation Decision Rule
0 out of 3	Enter 3 patients at the next dose level
1 out of 3	Enter 3 more patients at this dose level. 
 If 0 of these 3 patients experience DLT, proceed to the next dose level If 1 or more of this group suffer DLT, then dose escalation is stopped. Three (3) additional patients will be entered at the next lowest dose level if only 3 patients were treated previously at that dose.

≥ 2	Dose escalation will be stopped. Three (3) additional patients will be entered at the next lowest dose level if only 3 patients were treated previously at that dose.
DLT = dose limiting toxicity; MTD = maximum tolerated dose	

If a patient terminates the infusion of EGFRvIII CAR T cells prematurely or is lost to follow-up during the first 4 weeks after CAR treatment without experiencing a DLT, then the patient will not be evaluable for the determination of the MTD and will be replaced. The MTD is the highest dose level at which ≤ 1 of 6 patients experiences DLT during the 4 week observation period after CAR treatment. The last patient in a given cohort, receiving that dose level, should be observed for DLTs for at least 4 weeks prior to moving on to the next cohort/higher dose. Section 9.1.2 provides information about what constitutes a DLT.

An expanded cohort of a total of 12 patients will be enrolled at the MTD of EGFRvIII CAR T cells in order to obtain a more precise estimate of the probability of unacceptable toxicity. This cohort will also have the cells radiolabeled with ^{111}In to track their distribution. Briefly, CARs will be counted and re-suspended in PBS. $4\text{-}6 \times 10^8$ cells will be labeled with 500 micro Ci of ^{111}In . The cells will be washed and mixed with cold CARs to achieve the desired cell dose with a total of 500 μCi of ^{111}In . The labeled CARs will be infused into the patient through an intravenous catheter within the Ambulatory Bone Marrow Transplant (BMT) Unit. Distribution of ^{111}In -labeled EGFRvIII CARs will be evaluated at 1, 2, and 3 days post-infusion using whole body planar imaging followed by SPECT/CT, when indicated.

In the rare event that a sufficient amount of CAR-specific T cells cannot be generated for a patient's intended dose within the dose-escalation portion of this study, the patient will be treated at a lower pre-defined dose level using available CAR-specific T cells. If this patient experiences a DLT, data will be carefully reviewed to determine its impact upon dose escalation and future patient treatment. If this situation occurs with the expanded cohort, all available cells will be administered.

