Patients without definitive disease progression who remain eligible will then receive up to 3 cycles of dose-intensified (DI) TMZ at 50-100 mg/m²/day. Each full cycle of DI TMZ is 50-100 mg/m²/day for 21 days every 28 days, at the discretion of the treating physician. The purpose of the DI TMZ cycles is to achieve grade 3 lymphopenia. If the patient is able to tolerate the TMZ, they will receive 3 full cycles of DI TMZ prior to receiving the CAR T cells. If the patient is unable to complete the 3 cycles of DI TMZ, but has achieved grade 3 lymphopenia, they may receive CAR treatment at the discretion of the study PI and/or treating oncologist. If the patient's grade 3 lymphopenia subsides during the ~2 weeks it takes to produce the CAR T cells and before the scheduled receipt of CAR T cells, the treating physician has the discretion to re-initiate TMZ to re-establish grade 3 lymphopenia. If the patient is unable to tolerate the 3 full cycles of TMZ and does not reach grade 3 lymphopenia, or if the CAR-specific T cells do not meet release criteria, the patient will be withdrawn before CAR treatment and replaced.

Two weeks prior to CAR T cell administration, the patient must be on stable or decreasing steroids (≤ 4 mg/day). If patients are decreasing steroid use, once they are at 2 mg/day, they may be supplemented with hydrocortisone, at the discretion of the treating oncologist.

At least 48 hours after the patient's last dose of TMZ, the total dose of EGFRvIII CAR T cells will be delivered intravenously. If sufficient CAR-specific T cells cannot be generated to meet the targeted assigned dose within the dose-escalation portion of the study, the patient will be treated at a lower pre-defined dose level using available CAR-specific T cells and replaced in the assigned higher dose. The administered dose will be the highest defined dose level for which there are sufficient CAR-specific T cells available. Within the expanded cohort, if sufficient CAR-specific T cells can't be generated to meet the MTD dose, all available T cells will be administered.

Blood samples for immune monitoring (9 yellow, 1 red) will be drawn prior to EGFRvIII CAR infusion, 1, 5, 10, and 28 days after the infusion, then 3 and 6 months, then yearly until progression (or death or lost to contact). The return visits for immune monitoring at the 3 months, ~6 months, and ~yearly will

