10.4.2 Release Criteria for EGFRvIII CARs

Tests performed on the final product:

Table 5. Release Criteria for EGFRvIII CARs

Test	Method	Limits	Result	Initials/Date
-------------	---------------	---------------	---------------	----------------------

Cell viability ¹	Trypan blue exclusion	>70%		
Total viable cell number ¹	Visual microscopic count	>1 x 10 ⁷		
Tumor reactivity ²	γ-IFN release vs. EGFRvIII antigen	>200 pg/ml		
CAR expression ²	FACS analysis of the transduced cells	PBL >10%		
Microbiological studies	Gram stain ^{1,3}	No micro-organisms seen		
	Aerobic culture ^{3,4}	No growth		
	Fungal culture ^{3,4}	No growth		
	Anaerobic culture ^{3,4}	No growth		
	Mycoplasma test ⁵	Negative		
Endotoxin	Limulus assay ¹	<5 E.U./Kg		
RCR	S+L-Assay ⁴ RCR-PCR ⁶	Negative		

In the event of a positive sterility test, after the product has been infused, the Principal Investigator or his or her designate will notify the treating physician and the patient. The FDA and IRB will be notified within 15 calendar days. The patient will be asked to be evaluated by a physician within 24 hours. If the patient has or develops a temperature >38.5 °C or clinical evidence of infection at the injection site (erythema or edema) or systemically, the patient will have samples of from the injection sites, along with blood, urine and sputum (if possible) sent for bacterial, fungal, culture and sensitivity testing and will be treated expectantly with antibiotics based on the sensitivities of the organisms identified from the immunization product and an independent infectious disease consultation will be obtained to guide further therapy. Any remaining lymphocytes will be sent for bacterial, and fungal, culture and sensitivity testing and endotoxin testing.

10.4.3 ¹¹¹In-labeled T cells

CARs are washed three times with PBS, assessed for viability, and counted. CARs are re-suspended in PBS. 4-6x10⁸ cells will be labeled with 500 micro Ci of ¹¹¹In. The cells will be washed and mixed with cold CARs to achieve the desired cell dose containing 500 micro Ci of ¹¹¹In. The cell concentration is adjusted to 2.5 x10⁷ cells per mL and resuspended in preservative free saline with 1% human serum albumin (Baxter Healthcare Corp., US License No 140 NDC0944-0490-0L) and placed into the appropriate size syringe for infusion.

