15.3 Treatments

The number of patients who receive EGFRvIII CAR treatment will be summarized by dose level.

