15.4 Primary Objective

Within this “3+3” phase I study, the primary objective is to determine the MTD of a single IV infusion of EGFRvIII CAR T cells in patients with newly-diagnosed WHO grade IV malignant glioma. Four dose levels will be considered based on transduced cells/kg: #1: 4.5×10^6 /kg, #2: 1.5×10^7 /kg, #3: 4.5×10^7 /kg, and #4: 1.5×10^8 /kg. The MTD is the highest dose level at which ≤ 1 or 6 patients experience dose-limiting toxicity during the 4 weeks after CAR infusion. Section 9.1.2 provides information about what constitutes a dose-limiting toxicity. Section 9.1.1 provides details concerning the determination of the MTD.

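### Does the cap of 1.0 × 10^10 total cells leave dose level 4 undefined, or out of order with level 3?

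*Combined protocol and SAP*

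**What the plan says.** Section 9.1.1 introduces Table 3 by saying that "4 dose levels will be considered based on transduced cells/kg", and the dose column of that table is headed in CAR-specific T cells. The entry for level 4, 1.5 × 10^8/kg, carries an asterisk. Its footnote reads "dose level #4), the calculated dose will be capped at" 1.0 × 10^10 total cells. The other three levels have no cap.

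Section 9.1 covers the patient whose product falls short of the assigned dose: the dose given is the "highest defined dose level for which there are sufficient CAR-specific T cells available".

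Table 5 in Section 10.4.2 has two separate release tests that bear on cell counts. One is "Total viable cell number", with a floor of 1 × 10^7. The other is CAR expression, by "FACS analysis of the transduced cells", with a limit of more than 10%.

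In the statistical part, Section 15.4 repeats that "Four dose levels will be considered based on transduced cells/kg" and lists level 4 without the cap, then adds that "Section 9.1.1 provides details concerning the determination of the MTD". Section 15.3 says that "The number of patients who receive EGFRvIII CAR treatment will be summarized by dose level". Section 15.5 likewise tabulates DLTs by dose level.

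**The concern.** The levels are set in transduced cells per kg, but the cap is written as a number of total cells, a term that no section defines. Table 5 treats the viable cell count and CAR expression as different measurements. With a release limit of 10%, the two counts can differ almost tenfold. A literal reader could therefore apply the cap to everything infused.

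Two things would then be at stake. First, a 3+3 design assumes that each level is a higher dose than the one before. If a capped level 4 delivered fewer transduced cells per kg than an uncapped level 3, the Table 4 rules would be escalating to a lower dose for those patients. Second, on any reading, heavier patients at level 4 do not receive 1.5 × 10^8/kg. If level 4 became the MTD, the DLT rate that Section 15.7 expects to estimate from 18 patients would carry a per-kg label that some of them did not receive.

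**Working it through.** **Inputs from the documents.** Level 3 is 4.5 × 10^7/kg, level 4 is 1.5 × 10^8/kg and the cap is 1.0 × 10^10 (Section 9.1.1, Table 3). The CAR-positive fraction *f* must exceed 10% for release (Table 5).

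**Assumptions.** Body weight *w* is not given and Section 11 sets no weight limit, so 60 to 100 kg is used for illustration. No expected value of *f* is given for this product. The plan states no weight at which the cap starts to bind, so there is no figure of its own to reproduce.

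**Reading A: the cap counts transduced cells.**

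- The cap binds when 1.5 × 10^8 × *w* > 1.0 × 10^10, that is, above 1.0 × 10^10 / 1.5 × 10^8 = 66.7 kg.
- Above that weight the delivered dose is 1.0 × 10^10 / *w*.

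| Weight | Delivered per kg | Shortfall from label | Ratio to level 3 |
|---|---|---|---|
| 70 kg | 1.43 × 10^8 | 5% | 3.17 |
| 80 kg | 1.25 × 10^8 | 17% | 2.78 |
| 100 kg | 1.0 × 10^8 | 33% | 2.22 |

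- The uncapped ratio of level 4 to level 3 is 1.5 × 10^8 / 4.5 × 10^7 = 3.33.
- Level 4 would equal level 3 only at 1.0 × 10^10 / 4.5 × 10^7 = 222 kg.

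**Reading B: the cap counts all infused cells.**

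- The transduced dose per kg at the cap is *f* × 1.0 × 10^10 / *w*, and the cap binds above 66.7 × *f* kg.
- Level 4 falls below level 3 when *f* < 4.5 × 10^7 × *w* / 1.0 × 10^10 = 0.0045 × *w*. That is 27% at 60 kg, 31.5% at 70 kg, 36% at 80 kg and 45% at 100 kg.
- At 70 kg, level 4 delivers 1.43 × 10^7/kg at *f* = 10% (below level 2, 1.5 × 10^7/kg), 2.86 × 10^7/kg at 20%, and 7.14 × 10^7/kg at 50% (above level 3).

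**Which reading the text supports.** Four places point to A:

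- The sentence introducing Table 3 fixes the unit as transduced cells per kg.
- The dose column is headed in CAR-specific T cells.
- The footnote limits the calculated dose, which can only be that per-kg figure multiplied by weight.
- Section 9.1 speaks of the total dose of CAR T cells when it means the whole infusion, so the word total in the footnote most plausibly means not per kg.

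For B there is one place, Table 5. It is a product-release test with a floor of 1 × 10^7 and it does not define dose. B also requires one sentence to calculate a dose in one unit and limit it in another.

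**The case for a change.** The case for amending the text is that reading A is still an inference. The cross-reference in Section 15.4 leads back to the section holding the undefined term, so it does not settle the unit. Reading B would put products that pass release out of order. It would also clash with the Section 9.1 rule on short products, since a patient could count as level 4 on fewer transduced cells per kg than level 3 requires. Even on reading A, no section asks for the delivered dose, and Section 15.6 may model phenotypes by dose without saying whether nominal or delivered dose is meant. A clarifying phrase would cost almost nothing.

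The factual part stands: the unit of the cap is not spelled out, and level 4 is a flat dose above 66.7 kg. The consequence is much weaker. Reversed order needs three things together: level 4 is reached, staff adopt the mixed-unit reading, and the CAR-positive fraction lies below about 0.0045 × weight. The 10% limit is a floor, not an expected value. The 17% to 67% gene-transfer range in Section 7.2.5 comes from a melanoma T-cell receptor trial of a different product.

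The flat dose above 66.7 kg is what any ceiling on a per-kg dose produces, and it is disclosed on the table row it affects. Section 15.4 need not repeat a footnote in the section it cites. Tabulating by dose level matches the way the 3+3 rules and the MTD are defined. Viable count and CAR expression are already measured for each product, so an analyst can show delivered transduced cells per kg beside the nominal level without being told to.

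**Conclusion.** No change to the plan follows. The missing word is a gap that the surrounding text fills, and the cap is a disclosed design choice. Followed on its natural reading, the plan keeps level 4 at 2.22 to 3.17 times level 3 for weights of 70 to 100 kg and preserves the order of levels up to 222 kg. The Table 4 decisions and the MTD rule are unaffected. If level 4 is declared the MTD, what was tested is that level with its printed cap, and a competent report would say so.

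This rests on the cap counting transduced cells, which the context favours but no section states outright. If the sponsor meant all infused cells, the order of levels 3 and 4 would depend on the CAR-positive fraction, and the footnote would have to be reconciled with Sections 9.1.1 and 15.4. The weights are assumed, so the share of patients affected by the cap cannot be estimated. The point has no effect unless level 4 is reached. Nothing here bears on what the dose or the cap ought to be.

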9.1.2 Definition of Dose-Limiting Toxicity (DLT)

The DLT observation period is the 4 weeks after EGFRvIII CAR T cell infusion. Toxicities will be graded according to the NCI CTCAE version 4 criteria. A DLT will be defined as any Grade IV event of any duration that is at least (possibly, probably, or definitely) attributable to EGFRvIII CARs, or any Grade III toxicity that is at least (possibly, probably, or definitely) attributable to EGFRvIII CARs that is not reversible within 4 weeks. DLT definition includes and will be reported to FDA all of the following:

- a. Any treatment-emergent CTCAE Grade 4 or 5 CRS.
- b. Any treatment-emergent CTCAE Grade 3 CRS that do not resolve to \leq Grade 2 within 7 days.
- c. Any treatment-emergent autoimmune toxicity \geq Grade 3.
- d. CTCAE grade 3-5 allergic reactions related to the study cell infusion.
- e. CTCAE grades 3 and greater organ toxicity (cardiac, dermatologic, gastrointestinal, hepatic, pulmonary, renal/genitourinary, or neurologic) not pre-existing or due to the underlying malignancy and occurring within 30 days of study product infusion.

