The infusion of antigen reactive T cells may cause tumor lysis syndrome, a group of complications from release of large amounts of potassium, phosphate, and nucleic acid caused by the breakdown of tumor cells after cancer treatment. Tumor lysis syndrome may cause kidney failure, abnormal heart rhythm, and may even lead to death.

Cerebral Edema

Cerebral edema may be secondary to the disease process itself, the surgical procedure, necrosis from previous radiation, or inflammation due to immune infiltration of the brain or destruction of tumor cells. Symptoms may include, but are not limited to, severe headache, confusion, lethargy, unresponsiveness, coma, or focal neurological deficits. Patients will be monitored throughout the course of the study and those patients with any signs or symptoms of cerebral edema may need their steroid doses increased, treatment with an osmotic diuretic, or surgical decompression. Edema that fails to respond to aggressive therapy may lead to permanent neurological impairment. The probability of this risk can be predicted to some degree based upon tumor size, location, pre-operative neurological impairment, and post-operative course prior to EGFRvIII CAR T cell infusion. Patients will be monitored throughout the course of the study.

Infection

The EGFRvIII CAR T cells may include the risk of infection due to potential contamination of the cells in the laboratory. This may result in localized redness, swelling, or induration at the infusion site. In the most extreme situation, this may lead to systemic bacterial/fungal sepsis and possibly death. The probability of this risk is relatively low, given the fact that the cells will be strictly tested for sterility prior to each infusion. The risk of infection due to potential contamination of the cells in the laboratory will be minimized by biosafety quality assurance and testing. All cell cultures will be handled under sterile conditions in a core tissue culture facility dedicated to the processing of human cells. Prior to infusion into patients, EGFRvIII CAR T cells must pass sterility tests. Following infusions, patients will be monitored throughout the course of the study for any signs and symptoms of infection. If an active infection is suspected, patients will be cultured and treated with appropriate antibiotics.

RCR

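### When a CAR-related death is the only DLT among three patients, Table 4 sends three more to that dose, and no supplied text makes infusions wait for a review

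*Combined protocol and SAP*

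**What the plan says.** **Escalation rule (9.1.1, Table 4).** With one DLT in three patients: "Enter 3 more patients at this dose level". Then: "If 0 of these 3 patients experience DLT, proceed to the next dose level". With two or more DLTs, escalation stops. The grade of the DLT plays no part.

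**MTD and expansion (9.1.1).** The definition begins "The MTD is the highest dose level at which" and sets the limit at no more than 1 of 6 patients with a DLT in the 4-week window. Then: "An expanded cohort of a total of 12 patients will be enrolled at the MTD". Table 4 is written for escalation, and no corresponding rule is given for the expansion.

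**What counts as a DLT (9.1.2).** The general sentence opens "A DLT will be defined as any Grade IV event of any duration" and adds attributable Grade III toxicity that does not reverse within 4 weeks. Five listed items follow. Item (a) reads "Any treatment-emergent CTCAE Grade 4 or 5 CRS". Items (c), (d) and (e) cover autoimmune toxicity, allergic reactions and organ toxicity from Grade 3 upwards.

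**Oversight.** The PI-sponsor may terminate the study (9.5), and the PI may withdraw a subject (12.7.1). SAEs are reported at once to study leadership and go to FDA and IRB (13.3.1). The PI reviews adverse events periodically (13.1.1). SOCom review is annual (13.4). Extra monitoring is possible (14.1). Changes for an immediate hazard need no prior IRB approval (16.6). Section 16.5 refers to the DCI Data and Safety Monitoring Plan and to a fuller protocol-specific description held in eIRB.

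**The concern.** A treatment-related death in a cell-therapy trial calls for someone to look at the case before the next patient is infused. Here, when the death is the sole DLT in three, the one dosing instruction on paper is to carry on at that dose, and a clean second group of three leads to a higher one. Whether infusions pause rests on individuals choosing to use a general power.

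The scenario is not remote from the protocol's own account. Sections 7.2.5 and 7.2.7 describe a patient, the first treated in an anti-Her-2 CAR study, who died four days after infusion. The target there was different, and 7.2.7 expects no recognition of normal cells by the present product. But the statement in 9.2 that the dose was safe in recurrent glioma concerns the starting dose only, and levels 2 to 4 lie above it.

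At stake is the safety of the next patients. The statistical properties of the 3+3 design are not in question.

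**Working it through.** The plan states no figure on this point, so the check is a trace of the written rule and a search for any text that interrupts it.

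**Step 1. How a death enters the count.** Item (a) of 9.1.2 puts Grade 5 CRS beside Grade 4. Item (d) spans Grades 3 to 5. Items (c) and (e) start at Grade 3 with no upper limit. A death captured by any of these is one DLT, with the same weight as a survivable one.

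**Step 2. Trace through Table 4, with the death as the only DLT.**
- 1 of 3: three more patients at the same dose.
- 0 of those 3, so 1 of 6 overall: next dose level. At level 4 there is none.
- 1 of 6 meets the MTD definition. The dose becomes the MTD if it is level 4 or if the level above fails, and the 12-patient expansion follows.

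**Step 3. Infusions the text allows after the death.** These are counts from the protocol; no death rate is assumed.
- Death in the first patient at a level: (3 − 1) to complete the group + 3 under Table 4 = up to 5 more at that dose.
- If those are clean and a higher level exists: 3 to 6 patients there.
- If the dose becomes the MTD: 12 in expansion.
- Death in the first expansion patient: 12 − 1 = up to 11 more, with no written rule.

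**Step 4. Does any supplied text make the next infusion wait?**

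| Section | What it provides | Hold on other patients' infusions? |
|---|---|---|
| 9.1.1 | 4 weeks' observation of the last patient before the next, higher cohort | No; not triggered by a death, and not a review |
| 9.1.1 | Data review after a DLT in a patient moved to a lower level for lack of cells | No hold stated; special case only |
| 9.5 | Termination by the PI-sponsor | Discretionary |
| 12.2 | Postponement for fever or infection | Concerns that patient's own condition |
| 12.7.1 | Withdrawal of a subject by the PI | Discretionary, subject by subject |
| 13.1.1 | Periodic PI review; an amendment is considered if a trend appears | No |
| 9.1.2, 13.3.1 | Reporting; unexpected fatal events to FDA within 7 calendar days | No |
| 13.4 | Annual SOCom review, with stopping rules where applicable; none is given | No |
| 14.1 | Additional monitoring may be prompted | Optional |
| 16.6 | Immediate-hazard changes allowed | Permitted, not required |

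**Step 5. Deaths outside the list.** The general DLT sentence names Grades III and IV. A related Grade 5 event outside items (a) to (e) is therefore not expressly a DLT unless it was first graded IV. Sepsis from contaminated product is an example. Section 9.1.3 says of infection: "In the most extreme situation, this may lead to systemic bacterial/fungal sepsis and possibly death". Sepsis is not among the seven organ classes of item (e). If such a death within 4 weeks were not called a DLT, the literal text of 15.1 would drop the patient from the MTD Analysis Set for incomplete follow-up.

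**The case against.** **The hold may exist elsewhere.** Section 16.5 relies on an institutional plan and a protocol-specific description that were not supplied. This stands, and it limits the claim to the text at hand. If either document contains a hold, the remedy shrinks to a cross-reference.

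**The people who can stop the study hear at once.** SAEs go immediately to study leadership, who can terminate the study or withdraw the next patient. This also stands: a pause in practice is likely. But a power to stop is not a requirement to review before resuming.

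**Newly entered patients are far from infusion.** A patient entered after the death still faces leukapheresis, about 6 weeks of chemoradiation and up to three DI TMZ cycles. With all three cycles that is at least 42 + (28 + 28 + 21) + 2 = 121 days, about 17 weeks, which leaves ample time for a review. This is fair for the three extra patients if they are newly consented. It does not cover cohort-mates, expansion patients or others already well advanced in preparation. No stagger between patients within a cohort is written.

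**Fatal sepsis would be counted anyway.** Section 9.1.2 says its definition includes the listed items, and fatal sepsis would ordinarily bring Grade 3 or worse organ toxicity. Most investigators would count it. A reader might infer that the protocol ignores such deaths, and the text does not support that. It supports only that Grade V is not named where it should be.

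**A hold needs limits.** Treated patients are followed for up to 15 years (12.5), and cerebral edema may come from disease, radiation or cells (9.1.3). An open-ended trigger could halt the trial for late, ambiguous deaths. This stands, and the fix below sets a window.

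**Conclusion.** The point holds on the protocol text. A related death that is the sole DLT in three leads by rule to three more patients at that dose. If they are clean, it leads to escalation, or to an MTD with a 12-patient expansion that has no stopping rule. Stopping or pausing is discretionary throughout. The size is the count of infusions the text lets proceed: up to 5 at the same dose after a first-patient death at a level, and up to 11 after a first-patient death in expansion. The lack of Grade V in the general DLT sentence is a smaller, related gap.

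Three stronger readings are not supported:
- A reader might infer that the protocol tells investigators to continue after any related death. It does so only when the death is the sole DLT; with two or more DLTs, Table 4 stops escalation.
- A reader might infer that nothing protects patients. Several safeguards exist; what is missing is a required pause.
- A reader might equate the level-4 cap of 1.0 x 10^10 cells with the dose in the fatal anti-Her-2 case. The cap is stated in total cells while the dose levels are in transduced cells, so the documents do not establish that the two are comparable.

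The change is worth making because it is cheap and guards against an outcome nobody would defend. Confidence is medium, mainly because the plans cited in 16.5 could not be read.

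**What to change.** 1. In 9.1.2, extend the opening of the general DLT sentence so that attributable Grade V events are named alongside Grade IV.
2. In 9.1.1 (with Table 4) and 13.4, add a hold for escalation and expansion alike. The trigger is any death within 30 days of infusion judged at least possibly related to EGFRvIII CARs, or a later death judged probably or definitely related. Further infusions are then suspended until an ad hoc SOCom review is documented and agrees to resumption. Table 4 then applies unchanged.
3. If the DCI plan or the protocol-specific plan in eIRB already requires this, cite it in 9.1.1 instead of adding the hold.

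The 30-day window matches item (e) of 9.1.2. The higher bar for later deaths keeps long survival follow-up from triggering holds on weak attribution.

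**Cost.** The cost is protocol wording and, only if such a death occurs, an extra meeting of an existing committee and a temporary pause. During the pause, patients already prepared may miss the infusion window of 48 h (+72 h) after TMZ (Section 12), need TMZ re-initiated to restore lymphopenia (9.1), or lose product; formulated In-111-labeled cells are discarded after 6 hours (10.4.3). The 3+3 counts and the MTD rule do not change.
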